## **6 PATIENT ELIGIBILITY**

Investigators are responsible for confirming patient eligibility and will be required to maintain a log that includes limited information about all screened patients (initials, age, race, and sex; as allowed per local regulations) and outcome of screening.

### **6.1 Inclusion Criteria**

#### *Screening (Visit 1)*

For inclusion in the trial, patients must fulfill ALL of the following criteria:

- 6.1.1 Male or female, aged 18 years or above.
- 6.1.2 Willing and able to give informed consent for participation in the trial (see [Section 15.2](#)).
- 6.1.3 Willing and able (in the investigator's opinion) to comply with all trial requirements.
- 6.1.4 Has had a diagnosis with any disease subtype of MS, by revised 2017 McDonald criteria, for at least 12 months prior to Visit 1 and is expected to remain stable for the duration of the trial.
- 6.1.5 Has an MAS untransformed score of at least 2 in 2 or more of 6 muscle groups (right knee flexors, left knee flexors, right knee extensors, left knee extensors, right plantar flexors, or left plantar flexors) at Visit 1.
- 6.1.6 If currently receiving approved anti-spasticity therapy, it must be with a stable dosing regimen for at least 30 days prior to Visit 1. The patient must be willing to maintain the same antispasticity medication and not plan to initiate a new course of physiotherapy for the duration of the trial.
- 6.1.7 If currently receiving an approved MS disease-modifying therapy, it must be at a stable dose for at least 3 months prior to Visit 1 and is expected to remain stable for the duration of the trial.
- 6.1.8 If currently receiving dalfampridine or fampridine, it must be at a stable dose for at least 3 months prior to Visit 1 and is expected to remain stable for the duration of the trial.
- 6.1.9 Willing to allow the responsible authorities to be notified of participation in the trial, if mandated by local law.
- 6.1.10 Willing to allow his or her primary care practitioner (if he or she has one) and/or treating neurologist (if he or she has one) to be notified of participation in the trial, if the primary care practitioner/treating neurologist is different from the investigator.

*Additional Inclusion Criteria at Randomization (Visit 2)*

Patients are eligible for randomization in the trial if, in addition to continuing to meet the Screening (Visit 1) inclusion criteria, they also meet the following criterion prior to Visit 2 (Day 1):

6.1.11 Completed at least 5 of 7 days of their electronic diary reporting during the 7 days immediately preceding Visit 2 (Day 1).

## **6.2 Exclusion Criteria**

The patient may not enter the trial if ANY of the following apply:

- 6.2.1 Has taken nabiximols, cannabis, or a cannabis-derived product for medicinal or recreational purposes in the 30 days prior to Visit 1 or unable to abstain for the duration of the study.
- 6.2.2 Did not tolerate or did not respond adequately to treatment with nabiximols or another cannabis-based medication if exposed at any time before the 30-day period prior to Visit 1.
- 6.2.3 Any concomitant disease or disorder that has spasticity-like symptoms or that may influence the patient's level of spasticity.
- 6.2.4 Medical history suggests that relapse/remission is likely to occur during the trial, which, in the opinion of the investigator, is expected to influence the patient's spasticity.
- 6.2.5 Has had a relapse of MS within the 60 days prior to Visit 1.
- 6.2.6 Currently using botulinum toxin injection for the relief of spasticity (within 6 months of Visit 1) or is unwilling to abstain for the duration of the trial.
- 6.2.7 Currently taking antipsychotic medication.
- 6.2.8 Currently taking benzodiazepines unless doses and dosing regimen have been stable for at least 30 days prior to Visit 1.
- 6.2.9 Clinically suspected to have a contracture in one of the muscle groups of the lower limbs, preventing assessment with the MAS.
- 6.2.10 Has any known or suspected hypersensitivity to cannabinoids or any of the excipients of the IMP.
- 6.2.11 Has experienced myocardial infarction or clinically significant cardiac dysfunction within the last 12 months prior to Visit 1 or has a cardiac disorder that, in the opinion of the investigator, would put the patient at risk of a clinically significant arrhythmia or myocardial infarction.
- 6.2.12 Has a diastolic blood pressure of < 50 mmHg or > 105 mmHg or systolic blood pressure < 90 mmHg or > 150 mmHg (when measured in a sitting position at rest

for 5 minutes) or a postural drop in the systolic blood pressure of > 20 mmHg at Visit 1 or Visit 2. All measurements will be performed singly and can be repeated once, if any are outside the reference range but not considered clinically significant.

6.2.13 Has clinically significant impaired renal function at Visit 1, as evidenced by an estimated creatinine clearance lower than 50 mL/min. All measurements will be performed singly and can be repeated once, if any are outside the reference range but not considered clinically significant.

6.2.14 Has moderately impaired hepatic function at Visit 1, defined as serum alanine aminotransferase (ALT) or aspartate aminotransferase (AST) > 2 × upper limit of normal (ULN). All measurements will be performed singly and can be repeated once, if any are outside the reference range but not considered clinically significant.

6.2.15 Male and fertile (i.e., after puberty unless permanently sterile by bilateral orchectomy) unless willing to ensure that he uses male contraception (condom or vasectomy) or remains sexually abstinent during the trial and for 3 months thereafter.

6.2.16 Female and of childbearing potential (i.e., following menarche and until becoming postmenopausal for ≥ 12 consecutive months unless permanently sterile by hysterectomy, bilateral salpingectomy, or bilateral oophorectomy) unless willing to ensure that she uses a highly effective method of birth control (e.g., intrauterine device/hormone-releasing system, bilateral tubal occlusion, vasectomized partner, or sexual abstinence) during the trial and for 3 months thereafter. Patients using combined hormonal methods or a progestogen-only pill or injection or implant should use an additional barrier method such as a condom or diaphragm during the trial and for 3 months thereafter (see [Section 9.2.2](#)).

6.2.17 Female and pregnant (positive pregnancy test at Visit 1 or Visit 2), lactating, or planning pregnancy during the course of the trial or within 3 months thereafter.

6.2.18 Has received an IMP within the 30 days prior to Visit 1.

6.2.19 Has any other clinically significant disease or disorder (including seizure disorder) that, in the opinion of the investigator, may put the patient, other patients, or site staff at risk because of participation in the trial, may influence the interpretation of trial results, or may affect the patient's ability to take part in the trial.

6.2.20 Has any abnormalities identified following a physical examination, clinical laboratory, serology, or other applicable screening procedures that, in the opinion of the investigator, would jeopardize the safety of the patient or the conduct of the study if he or she took part in the trial.

- 6.2.21 Has any history of suicidal behavior in the 5 years prior to Visit 1 or a score of 3, 4, or 5 on the C-SSRS in the month prior to Visit 1.
- 6.2.22 Has donated blood during the 3 months prior to Visit 1 and is unwilling to abstain from donation of blood during the trial.
- 6.2.23 Has been previously randomized into this trial.
- 6.2.24 Has any known or suspected history of alcohol or substance abuse (including opiate abuse) or dependence within 1 year prior to Visit 1.
- 6.2.25 Currently using an illicit drug or current nonprescribed use of any prescription drug.
- 6.2.26 Has a history of psychiatric or neurologic disorder that, in the opinion of the investigator, may interfere with trial participation, data interpretation, or conduct of trial procedures.
- 6.2.27 Has a history of severe psychiatric disorder that may be exacerbated by the use of a cannabinoid-containing product.
- 6.2.28 Has any planned clinical interventions or intends to change any or all medications that may have an effect on spasticity or MS during the trial.
- 6.2.29 Currently taking drugs that are solely metabolized by UGT1A9 and UGT2B7 (see [Appendix 4](#)).
- 6.2.30 Currently taking strong CYP3A4 inducers (e.g., rifampicin, carbamazepine, phenytoin, phenobarbital, St John's Wort).

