	

• Clinically suspected to have a contracture in one of the muscle groups of the lower limbs, preventing assessment with the MAS.

• Has any known or suspected hypersensitivity to cannabinoids or any of the excipients of the IMP.

• Has experienced myocardial infarction or clinically significant cardiac dysfunction within the 12 months prior to Visit 1 or has a cardiac disorder that, in the opinion of the investigator, would put the patient at risk of a clinically significant arrhythmia or myocardial infarction.

• Has a diastolic blood pressure of < 50 mmHg or > 105 mmHg or systolic blood pressure < 90 mmHg or > 150 mmHg (when measured in a sitting position at rest for 5 minutes) or a postural drop in the systolic blood pressure of > 20 mmHg at Visit 1 or Visit 2. All measurements will be performed singly and can be repeated once, if any are outside the reference range but not considered clinically significant.

• Has clinically significant impaired renal function at Visit 1, as evidenced by an estimated creatinine clearance lower than 50 mL/min. All measurements will be performed singly and can be repeated once, if any are outside the reference range but not considered clinically significant.

• Has moderately impaired hepatic function at Visit 1, defined as serum alanine aminotransferase (ALT) or aspartate aminotransferase (AST) > 2 × upper limit of normal (ULN). All measurements will be performed singly and can be repeated once, if any are outside the reference range but not considered clinically significant.

• Male and fertile (i.e., after puberty unless permanently sterile by bilateral orchectomy) unless willing to ensure that he uses male contraception (condom or vasectomy) or remains sexually abstinent during the trial and for 3 months thereafter.

• Female and of childbearing potential (i.e., following menarche and until becoming postmenopausal for ≥ 12 consecutive months unless permanently sterile by hysterectomy, bilateral salpingectomy, or bilateral oophorectomy) unless willing to ensure that she uses a highly effective method of birth control (e.g., intrauterine device/hormone-releasing system, bilateral tubal occlusion, vasectomized partner, or sexual abstinence) during the trial and for 3 months thereafter. Patients using combined hormonal methods or a progestogen-only pill or injection or implant should use an additional barrier method such as a male condom or diaphragm during the trial and for 3 months thereafter.

• Female and pregnant (positive pregnancy test at Visit 1 or Visit 2), lactating, or planning pregnancy during the course of the trial or within 3 months thereafter.

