#### **9.1.1 Screening (Visit 1 [Days -28 to -1])**

Informed consent (see [Section 9.2.1](#)) must be obtained from the patient prior to beginning any trial-related procedures.

The following assessments/procedures will be performed:

- Eligibility check ([Section 6](#))
- Demographics ([Section 9.2.3](#))
- Previous cannabis use ([Section 9.2.4](#))
- Medical history ([Section 9.2.5](#))
- Electronic diary training ([Section 9.2.14.1](#))
- Concomitant medications review ([Section 9.2.6](#))

- AE review ([Section 9.2.17](#))
- Physical examination (including height measurement; [Section 9.2.7](#))
- Oral mucosa examination ([Section 9.2.8](#))
- Body weight measurement ([Section 9.2.9](#))
- Vital signs measurement ([Section 9.2.10](#))
- 12-lead ECG ([Section 9.2.11](#))
- Clinical laboratory blood sampling (hematology and biochemistry) ([Section 9.2.12](#))
- Dipstick urinalysis ([Section 9.2.12](#))
- Urine drug screen (including THC) ([Section 9.2.12](#))
- Serum pregnancy test (if appropriate) ([Sections 9.2.2 and 9.2.12](#))
- Blood THC test ([Section 9.2.12](#))
- MAS assessment ([Section 9.2.15.1](#))
- C-SSRS assessment ([Section 9.2.15.3](#))

The investigator should review the laboratory results as soon as these become available. If the results show that a patient is ineligible, the patient will fail screening.

Following Visit 1, there will be no changes in the dosing regimen of the patient's current oral MS antispasticity medications (if any).

Patients who satisfy all of the inclusion criteria and none of the exclusion criteria specified in [Section 6](#) will enter a baseline period of at least 7 days prior to Visit 2, during which they will be required to take their oral antispasticity medication (if any) and complete an electronic daily diary to record their 11-point NRS spasticity score, spasm count, and use of antispasticity medications once daily, around the same time each day, preferably in the evening before retiring to sleep.

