### **9.2.10 Vital Signs**

As part of the screening procedures at Visit 1, vital signs (systolic and diastolic blood pressure and pulse rate) will first be measured after the patient assumed a supine position for 5 minutes. Vital signs will then be measured within 2 minutes of assuming a standing position in ambulatory patients only. At all subsequent time points, vital sign measurements will be completed in a sitting position at rest for 5 minutes. Blood pressure should be recorded using the same arm throughout the trial, where possible.

Additional vital signs measurements may be taken during the trial if clinically indicated.

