**SPONSOR: GW PHARMA LIMITED**

Study Code: GWSP20105  
 EudraCT Number: 2020-003271-18  
 GWSP20105 Protocol V1 22Jul2020

Period	Screening		Treatment Period 1				Treatment Period 2			Safety Follow-up
	Visit Number	Visit 1	Visit 2	Visit 3 (Phone C all)	Visit 4	Visit 5 a	Visit 6	Visit 7 (Phone Call)	Visit 8	
Day/Hour	Day -28 to -1	Day 1 predose	Day 1 2-4 hrs postdose	Day 8 ( $\pm 1$ day)	Day 15 ( $\pm 1$ day)	Day 21 ( $\pm 2$ days)	Day 31 predose ( $\pm 1$ day)	Day 38 ( $\pm 1$ day)	Day 45 ( $\pm 1$ day)	Day 51 ( $\pm 2$ days) End of Treatment Visit
MAS f	X	X	X			X	X			Day 58 (+3 days)
MSSS-88						X				X
T25FW test g		X				X	X			X
C-SSRS	X	X			X	X	X			X
IMP dosing training		X								
IMP dosing h		X				X	X			X
IMP dispensing i		X			X		X		X	
IMP collection and compliance review				X	X	X			X	

AE = adverse events; C-SSRS = Columbia-Suicide Severity Rating Scale; ECG = electrocardiogram; EoT = end of treatment; IMP = investigational medicinal product; MAS = Modified Ashworth Scale; MS = multiple sclerosis; MSSS-88 = Multiple Sclerosis Spasticity Scale; NRS = Numerical Rating Scale; PK = pharmacokinetics; T25FW = Timed 25-Foot Walk; THC =  $\Delta^9$ -tetrahydrocannabinol.

a A washout period of at least 7 days will separate the 2 treatment periods. Following the final dose of IMP in Treatment Period 1, in the morning of Visit 5 (Day 21), patients will discontinue treatment with IMP for the 7 days prior to Visit 6 (Day 31). During the washout period, patients will continue to take their current MS antispasticity medications without any changes in dose.

b A comprehensive physical examination, including an assessment of height, will be completed at Screening (Visit 1) only; subsequent physical examinations will be symptom-directed.

c Serum pregnancy test at Visits 1 and 10; urine pregnancy test at Visits 2 and 6 (predose).

d On the day before PK blood sampling at Visits 4, 5, 8, and 9, patients will be prompted to record whether they started their morning and evening doses of IMP within 30 minutes of a snack or meal. On the day of PK blood sampling, the exact time and date of PK blood sampling and the time of the patient's snacks and meals should be recorded. See Section 9.2.12.1 for the PK blood sampling schedule. Please note that more than one PK sample may be collected at distinct time points during a single visit.

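### Exclusion 6.2.12 tests for a postural systolic drop at Visit 1 or Visit 2, but Protocol 9.2.10 schedules postural readings only at Visit 1

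*Protocol*

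**What the plan says.** Protocol 6.2.12 sets limits on diastolic and systolic pressure measured sitting at rest. It then adds a second limb, a "postural drop in the systolic blood pressure of > 20 mmHg at Visit 1 or Visit 2". The synopsis carries the same criterion. Readings are taken singly, and one repeat is allowed when a value is out of range but not judged clinically significant.

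Protocol 9.2.10 fixes the posture of each scheduled reading. At Visit 1 the patient is measured after 5 minutes supine, and then: "Vital signs will then be measured within 2 minutes of assuming a standing position in ambulatory patients only". After that: "At all subsequent time points, vital sign measurements will be completed in a sitting position at rest for 5 minutes". The section ends with an allowance: "Additional vital signs measurements may be taken during the trial if clinically indicated".

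The Visit 2 predose list (Protocol 9.1.2.1) includes an eligibility check and a vital signs measurement and names no posture. None of the footnotes to the Schedule of Assessments (Protocol Appendix 1) deals with posture.

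SAP 12.7.4 describes vital signs as sitting values, planned at Screening as well as at the treatment and follow-up visits, and summarises the change from Screening to follow-up by treatment sequence. SAP 12.2.3 instead lists baseline blood pressure as a supine value and a supine-minus-standing difference. SAP 10.2 takes the most recent value before the first dose as the baseline for clinic-based safety endpoints.

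**The concern.** A postural drop is a difference between readings in two positions. Visit 2 is the day of randomization and first dosing, and eligibility has to be confirmed there before either happens. If only a sitting value is scheduled that morning, one limb of a stated safety exclusion has no scheduled data behind it at one of the two visits it names. Sites must then either add readings on their own initiative or leave that limb unchecked, and they may differ in which they do.

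The analysis has a smaller version of the same problem. A change score is interpretable only if both values were taken in the same way. Under 9.2.10 the Screening value is supine or standing and the follow-up value is sitting, so the planned Screening to follow-up summary would mix any change over time with a change of posture.

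**Working it through.** The documents state no figure to reproduce. The check sets the eligibility rule, the measurement schedule and the analysis side by side.

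**1. Postural readings against the visits named**

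| Visit | Needed for the postural limb of 6.2.12 | Scheduled by 9.2.10 | Drop derivable from scheduled readings? |
|---|---|---|---|
| Visit 1 | Two postures | Supine, then standing (ambulatory only) | Yes, in ambulatory patients |
| Visit 2 predose | Two postures | Sitting only | No |

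A scheduled postural reading therefore exists at 1 of the 2 visits named. Non-ambulatory patients have no scheduled standing value at any visit; 9.2.10 makes that restriction openly.

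**2. Does the wording require a check at both visits?** In an exclusion criterion, a drop at either visit excludes, so ruling the criterion out takes a check at each. Criterion 6.2.17 shows how the protocol handles the same phrase elsewhere: "Female and pregnant (positive pregnancy test at Visit 1 or Visit 2". There the schedule follows through: "Serum pregnancy test at Visits 1 and 10; urine pregnancy test at Visits 2 and 6 (predose". That criterion has one limb and so does not settle how 6.2.12 should be parsed, but it shows the phrase paired with a scheduled test at each visit.

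**3. Age of the postural reading at first dose.** Protocol 9.1.1 says eligible patients "will enter a baseline period of at least 7 days prior to Visit 2", so the minimum is about 7 days. The screening period is at most 28 days, so the maximum is about 28 days.

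**4. Screening to follow-up change**

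- Screening posture under 9.2.10: supine, and standing if ambulatory.
- Follow-up (Visit 10) posture under 9.2.10: sitting.
- Posture assumed by SAP 12.7.4 at both: sitting.
- Day 1 H0 posture under both 9.2.10 and SAP 12.7.4: sitting.

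The Screening value does not match the follow-up value in posture, and the Day 1 H0 value does. Day 1 H0 is also the value that the SAP 10.2 rule selects when the predose reading is present.

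**5. Time cost of adding the Visit 2 readings.** Five minutes supine plus standing within 2 minutes is up to about 7 minutes per patient. Applied to all 190 planned patients: 190 × 7 / 60 = 22.2 hours, over about 30 sites. This is an order of magnitude and not a bound. It counts non-ambulatory patients, who would not need the readings. It leaves out the repeats allowed by 6.2.12 and any additional patients enrolled under Protocol 4.3 if more than 20 withdraw.

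**The case against.** The strongest reply is that the exclusion can still be applied. The eligibility check is a scheduled Visit 2 procedure, so a diligent site would take whatever readings 6.2.12 needs, and 9.2.10 allows extra vital signs. That is correct as far as it goes. A reader might infer that the Visit 2 postural exclusion is impossible to apply, and the documents do not support that. They support only that it cannot be applied from the scheduled readings. The allowance in 9.2.10 depends on clinical indication, and the repeat in 6.2.12 depends on an out-of-range value. Neither schedules a second posture.

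A second reply is that the phrase naming the visits can be read distributively, with each limb tested at the visit where 9.2.10 schedules it. Taken in order, that reading assigns the sitting limits to Visit 1 and the postural drop to Visit 2, the reverse of 9.2.10, so it does not remove the conflict.

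A third reply concerns consequences, and most of it stands. Ambulatory patients have a postural check at Visit 1, and all patients have a sitting check at Visit 2. Background antispasticity therapy is required to be stable. The first dose is one supervised spray, followed by vital signs and adverse event review at 2 to 4 hours. Criteria 6.2.19 and 6.2.20 let the investigator exclude any patient judged at risk. SAP Appendix 1 does not list 6.2.12 among the major important deviations.

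On the SAP point, the case report form is not in the documents, so a sitting Screening value may have been collected. The mismatch is inferred from 9.2.10, and SAP 12.2.3 is consistent with it.

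**Conclusion.** Two stated rules conflict on a safety exclusion checked before first dosing: 6.2.12 names Visit 2 for the postural drop, and 9.2.10 schedules only a sitting reading there. Separately, SAP 12.7.4 assumes a sitting Screening value that the protocol does not schedule.

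The effect is small. It concerns one limb of one criterion at one of two visits, in ambulatory patients, plus one descriptive summary. The documents give neither the ambulatory share of the roughly 190 planned patients nor the rate of new postural drops between visits, so no count of affected patients can be given. A reader might infer that patients with a postural drop were dosed as a result. Nothing in the documents shows this. Efficacy is unaffected.

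The conclusion rests on taking the visit phrase to cover at least the postural limb, which it directly follows. If it also covers the sitting limits, the same kind of gap exists at Visit 1, where no sitting reading is scheduled; the main point does not depend on that.

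**What to change.** **Protocol.** Choose one:

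- In 9.2.10 and the Schedule of Assessments, add supine then standing readings at Visit 2 predose for ambulatory patients. This costs a few minutes of existing staff time per patient, plus data fields for the readings.
- If the postural check was meant for screening only, limit the postural limb of 6.2.12 and its synopsis copy to Visit 1. This is a wording change with no added visit time.

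Either needs a protocol amendment, handled under Protocol 16.1. The SAP addendum (section 6.0) records the decision of 9 November 2022 to stop the study and halt enrollment, so neither option can now change conduct in this trial. They apply to the plan as written and to any protocol that reuses this text.

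**SAP 12.7.4.** Use the sitting Day 1 H0 value, which is the SAP 10.2 baseline, as the reference for the follow-up change. This can still be done. The addendum's reporting table lists vital signs among the safety outputs and appears to keep them as set out in the SAP, although its layout is broken in the available text. No new data are needed; the cost is one sentence in the SAP and one changed reference in programming.
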